7.2. Secondary Growth Analyses

Secondary analyses pertinent to growth will be provided and are detailed. All secondary analyses described in the following sections will be based on the Growth Population, as defined in Section 4: Analysis Populations, unless otherwise specified.

7.2.1. Percentage of Participants with Growth Velocity Below the 3rd Percentile During the Double-Blind Treatment Period

The number and percentage of participants whose growth velocity during the double-blind treatment period is below the 3rd percentile will be summarized by treatment and listed. Details of the calculation of these percentiles can be found in Section 11.6.3. This characterization of growth velocity will be based on all available on- and off-treatment height data.

No formal statistical analysis is planned.

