Evidence derived from a Cochrane meta-analysis of randomised trials shows that regular use of ICS at low or medium daily doses is associated with a mean reduction of 0.48 cm per year in linear growth velocity and 0.61 cm in change from baseline in height during a one-year treatment in children with mild to moderate persistent asthma. The effect size of ICS on linear growth velocity appears to be associated more strongly with the ICS molecule than device or dose (low to medium dose range). The ICS-induced growth suppression seems to be maximal in the first year of therapy and less pronounced in the subsequent years of treatment [Zhang, 2014]. Another Cochrane review of the literature concluded that in persistent asthma, a small but statistically significant group difference in growth velocity was observed between low doses of ICS and low to medium doses of HFA-beclomethasone equivalent, favouring the use of low-dose ICS [Pruteanu, 2014]. In the four comparisons reporting linear growth over 12 months, a significant group difference was observed, clearly indicating lower growth velocity in the higher ICS dose group of 5.74 cm/y compared with 5.94 cm/y on lower-dose ICS (N = 728 school-aged children; mean difference (MD) 0.20 cm/y, 95% confidence interval (CI) 0.02 to 0.39). The authors concluded that in view of prevailing parents' and physicians' concerns about the growth suppressive effect of ICS, lack of or incomplete reporting of growth velocity in more than 86% (19/22) of eligible paediatric trials including those using beclomethasone and budesonide, is a matter of concern.

Therefore, there is good evidence to suggest that the first year of treatment with an inhaled corticosteroids is the most critical phase with respect to growth. In view of the seasonal variations in growth, one year is the minimum duration to reliably measure annual growth velocity [Tillmann, 2001].

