4. ANALYSIS POPULATIONS

Population	Definition / Criteria	Analyses Evaluated
Total	
 Comprised of all participants screened and for whom a record exists on the study database. 	
 Study Population Safety
Intent-to-Treat (ITT)	
 Comprised of all randomised participants who receive at least one dose of study treatment. This population will be based on the treatment to which the participant was randomised. Any participant who receives a treatment randomisation number will be considered to have been randomised. 	
 Study Population Safety (including Growth Analyses) Efficacy
Growth	
 Comprised of all ITT participants who have stadiometric height assessments from at least three post-randomisation, on-treatment clinic visits (i.e., including all available height measurements after Visit 5 up to and including Visit 18, without exclusion) during the double-blind treatment period. Note: To be included in the Growth population, the 1st and 3rd height measurements need to be at least 7 weeks apart. 	
 Study Population Safety (i.e., Growth Analyses)

Refer to [Appendix 9](#): List of Data Displays which details the population used for each display.

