11.6.3. Growth Data

Triplicate stadiometric height measurements, as well as the average of each set of triplicate measurements, will be collected at each planned visit according to the Protocol Defined Schedule of Events (see Section 11.2.1). The average will serve as the participant’s height at that clinic visit.

Growth Data
Growth Velocity Calculation

 • Growth velocity will be calculated for each participant over each study period (i.e., baseline, double-blind treatment, and follow-up) by fitting a regression line to the height measurements recorded for that participant during the period. The slope of this regression line will be the participant’s growth velocity for that study period. • Stadiometric height measurements obtained at Visits 1, 3, and 5 will be used to determine the baseline period growth velocity, which will be calculated based on data from at least two of these visits. • Stadiometric height measurements obtained at Baseline (Visit 5) and during the double-blind treatment period (Visit 6 up to and including Visit 18) will be used to determine the double-blind treatment period growth velocity. Separate estimands for growth velocity during the double-blind treatment period will be considered in the Growth and ITT populations (as defined in Section 7.1: Primary Growth Analyses). • Stadiometric height measurements obtained at Visits 18 and during the follow-up period will be used to determine the follow-up period growth velocity. • Stadiometry measurements obtained during the Early Withdrawal/Early Treatment Discontinuation Visit will be included in the calculation of the growth velocity over the double-blind treatment period.
Growth Velocity Below the 3rd Percentile

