
 • Using Table VIIA and Table VIIB in Standards from Birth to Maturity for Height, Weight, Height Velocity, and Weight Velocity: British Children, 1965 Part II (Tanner, 1966) data values for the 3rd percentile for growth velocity will be input into an Excel spreadsheet and then imported into the SAS programming environment. • Each participant’s double-blind treatment period growth velocity, calculated based on all on- and off-treatment height data, will be programmatically compared to these imported data using the 3rd percentile value of the age closest to the participant’s age at the end of the endpoint (i.e., either the end of the participant’s double-blind treatment period [Visit 18] or withdrawal from study [Early Withdrawal Visit]).
Change from Baseline in Growth Velocity Quartiles

 • Growth velocity quartile (defined as 1Q = 1st – 25th percentile, 2Q = 26th – 50th percentile, 3Q = 51st – 75th percentile, 4Q = 76th – 100th percentile) will be determined for each participant at both baseline and endpoint. • Baseline growth velocity will be calculated as the slope from a simple linear regression of the average stadiometric height measurements recorded at Visits 1, 3, and 5. • Endpoint growth velocity will be defined as the slope of a simple linear regression of the average stadiometric height measurements recorded at Visit 12 up to and including Visit 18 and will include both on- and off-treatment measurements. • Using Table I in Special Article: Clinical longitudinal standards for height and height velocity for North American children (Tanner, 1985) and Table VIIA and Table VIIB in Standards from Birth to Maturity for Height, Weight, Height Velocity, and Weight Velocity: British Children, 1965 Part II (Tanner, 1966), data values for the 25th, 50th, and 75th growth velocity percentiles will be input into an Excel spreadsheet and then imported into the SAS programming environment.

- Each participant’s baseline period growth velocity will be programmatically compared to these imported data using the participant’s estimated age at Visit 5 and age in the imported data that is closest to the actual age of the participant to determine the participant’s baseline growth velocity quartile.

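### The below-3rd-percentile count tests 12-week slopes against the same annual cut-off as 52-week slopes, so normally growing children whose heights stop at about Week 12 are flagged more often

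*SAP*

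**What the plan says.** - **Endpoint.** The proportion below the 3rd percentile of growth velocity is a named secondary endpoint of the primary objective (Protocol 3, SAP 2.2). SAP 7.2.1 reports it descriptively: "The number and percentage of participants whose growth velocity during the double-blind treatment period is below the 3rd percentile will be summarized by treatment". It adds: "This characterization of growth velocity will be based on all available on- and off-treatment height data".
- **Who is counted.** Section 7.2 uses the Growth Population: "Comprised of all ITT participants who have stadiometric height assessments from at least three post-randomisation, on-treatment clinic visits". SAP 4 adds one spacing rule: "To be included in the Growth population, the 1st and 3rd height measurements need to be at least 7 weeks apart".
- **Which heights enter the slope.** Under SAP 11.6.3 the treatment-period slope is fitted to Visit 5 and the heights up to Visit 18. Early Withdrawal and Early Treatment Discontinuation heights are included.
- **What the slope is compared with.** SAP 11.6.3: each child's "double-blind treatment period growth velocity, calculated based on all on- and off-treatment height data, will be programmatically compared to these imported data". The cut-off is the published 3rd percentile for the nearest age at the end of treatment or at the Early Withdrawal Visit. Early leavers are therefore classified by design, and the cut-off does not depend on the span.
- **The protocol's own premise.** Protocol 2.2, pointing to seasonal variation in growth, states that "one year is the minimum duration to reliably measure annual growth velocity".

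**The concern.** A child with heights at Visits 5, 6, 7 and 8 and nothing later meets the entry rule. Given the visit windows, the span can be slightly under 12 weeks. That child's slope is scaled to cm/yr and judged against the same percentile as a 52-week slope, although the protocol says less than a year is too short for a reliable annual velocity.

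For a mean, extra slope error costs precision. For a cut-off in the lower tail it acts in one direction: a wider spread pushes more normal children below the line than it lifts slow growers above it. The percentage then partly measures how many children lost their later heights. A reader of a paediatric growth-safety report will take it as the share growing abnormally slowly.

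The rest of the plan does not cover this. The completers' analysis (Supportive Estimand VII) and the two imputation approaches (Estimands IX and X) concern mean velocity only. Elsewhere the SAP does set a time anchor: the 12-week analysis needs a Visit 8 height, and the SDS change needs Visit 18. Section 7.2.1 sets none.

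**Working it through.** **Inputs from the documents.** Stadiometry at Weeks 0, 4, 8, 12, 16, 28, 40 and 52 (Protocol 7.1). Velocity SD 1.2 cm/yr and 203 evaluable children per arm (Protocol 9.2.1).

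**The plan's own figure.** Half-width = 1.96 × 1.2 × √(2/200) = 0.235, as in the table in Protocol 9.2.2. At 203 per arm the full width is 0.467, within the stated 0.5 cm/yr. The SD of 1.2 is therefore the value the plan works with.

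**Assumptions, not in the documents.** SD of the error in a visit's mean height, σ: 0.15 to 0.30 cm. As an alternative to 1.2, a true velocity SD of 0.7 to 0.9 cm/yr. Velocities are normal and distributed as in the reference standard.

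**Formulas.** Slope error SD = σ × 52.18/√Sxx, with Sxx in weeks². P(below 3rd) = Φ(−1.881 × SD / √(SD² + slope error²)).

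- Weeks 0, 4, 8, 12: mean 6, Sxx = 36 + 4 + 4 + 36 = 80, so 5.83 cm/yr per cm of error.
- All eight visits: mean 20, Sxx = 2368, so 1.07 cm/yr per cm.

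**One case in full (SD 1.2, σ 0.30).**

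- Week 12: slope error 0.30 × 5.83 = 1.75; total SD √(1.44 + 3.06) = 2.12; Φ(−1.06) = 14.4%.
- Week 52: slope error 0.30 × 1.07 = 0.32; total SD 1.24; Φ(−1.82) = 3.5%.
- Ratio 4.2.

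**All spans, σ 0.15 to 0.30 cm.**

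| Last height | Sxx | Error per cm | Flagged, SD 1.2 | Ratio to Week 52 | Flagged, SD 0.7–0.9 | Ratio to Week 52 |
|---|---|---|---|---|---|---|
| Week 12 | 80 | 5.83 | 6.4–14.4% | 2.1–4.2 | 8.9–24.2% | 2.8–5.5 |
| Week 16 | 160 | 4.13 | 4.7–9.5% | 1.5–2.7 | 6.1–17.7% | 1.9–4.1 |
| Week 28 | 493 | 2.35 | 3.6–5.2% | 1.1–1.5 | 4.0–9.3% | 1.2–2.1 |
| Week 40 | 1198 | 1.51 | 3.2–3.9% | 1.0–1.1 | 3.4–5.7% | 1.1–1.3 |
| Week 52 | 2368 | 1.07 | 3.1–3.5% | 1 | 3.2–4.4% | 1 |

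**Sensitivity of the Week 12 ratio.**

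- σ of 0.10 cm: 1.5 (SD 1.2) to 2.4 (SD 0.7).
- 1.2 taken as the SD of fitted one-year slopes, with 3.0% of those below the cut-off: 2.1 to 4.7 over σ 0.15 to 0.30, and 1.5 to 7.8 over σ 0.1 to 0.5.
- Sample one-year SD 1.2 against a narrower standard (assumed SD 0.8 to 1.0): 1.5 to 3.2, because children measured for a year are then flagged more often too.

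**Effect on the count (illustrative).** Suppose 10% of 203 children (20.3) have heights ending in equal parts at Weeks 12, 16 and 28.

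- SD 0.9, σ 0.15: mean rate (8.9 + 6.1 + 4.0)/3 = 6.3%; 20.3 × (6.3% − 3.2%) = 0.6 extra cases on an expected 6.5.
- SD 0.7, σ 0.30: (24.2 + 17.7 + 9.3)/3 = 17.1%; 20.3 × (17.1% − 4.4%) = 2.6 extra on 8.9.
- SD 1.2: 0.4 to 1.3 extra on 6.3 to 7.0.

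**The case against.** **The endpoint is descriptive and the exposed group may be small.** Both are true. The only rate in the documents, up to 10%, is withdrawal from study medication within the first 12 weeks, and Protocol 9.2.1 already removes those children in going from 450 randomised to 406. No rate is given for losing heights after Week 12. Protocol 5.5.1 asks sites to follow treatment stoppers, with emphasis on the 52-week height, and their off-treatment heights count here. Short slopes therefore come only from leaving the study or missing later heights.

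**The effect on the arm comparison is small.** With 10% early leavers in one arm and 5% in the other, the mix above shifts the comparison by 10.15 children × the same excess, or 0.2 to 1.3 cases. The chance SD of the difference, √(2 × 203 × p(1 − p)), is 3.5 to 4.1. A reader might infer that the FF-placebo comparison is biased; the documents do not show that. Equal withdrawal inflates both arms alike, and nothing in the plan predicts which arm would lose more heights.

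**Planned outputs already expose it.** Listing 30 names the flagged children, Listing 24 gives every height, and Table 2.25 counts missing heights by visit. These allow a reconstruction by hand, but no table links a flag to the length of its slope.

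**Restricting the count selects on retention.** This stands. If slow growth or poor asthma control leads to withdrawal, a restricted count drops true cases. It is the reason to add the restricted count and not to replace the planned one.

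**Conclusion.** The point holds for short slopes. Under the plan's rules, a normally growing child whose heights end at about Week 12 is flagged about 2 to 4 times as often as one measured to Week 52 (SD 1.2 cm/yr), or about 3 to 5.5 times (assumed true SD 0.7 to 0.9). Both ranges rest on an undocumented height error of 0.15 to 0.30 cm. The size moves with the assumptions; the direction does not change in any case examined.

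A reader might infer that early leavers in general are flagged at such multiples. The schedule does not support that. The ratio is about 1.5 to 4 at Week 16, 1.1 to 2.1 at Week 28 and at most 1.3 at Week 40. Children who stop treatment and keep attending to Week 52 are not affected.

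Both arms' percentages are inflated to the extent that children leave the study or lack later heights. The comparison is distorted only if that differs by arm in number or timing. With 6 to 9 cases expected per arm, one or two noise-driven cases are worth separating out. This is a cheap improvement to a secondary display and leaves the primary analysis untouched.

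**What to change.** In SAP 7.2.1 and 11.6.3, keep the planned all-children count in Table 2.26 and add, per arm:

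- (a) the number and percentage below the 3rd percentile among children with any height at Week 40 or later;
- (b) the number of children whose heights end before Week 40, and how many of them are flagged.

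Mark the short-span children in Listing 30. State that any claim about the share of slow-growing children rests on (a) read together with (b). Week 40 is a working choice, taken because the ratio there is at most 1.3 under the assumptions above.

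Cost: a few sentences of SAP text, two table rows and one listing flag, with no new data. The drawback is that (a) is conditional on staying in the study to Week 40, so true slow growers who leave early appear only in (b) and in the all-children count.

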7.2.2. Change from Baseline in Growth Velocity Quartiles

Shifts from baseline to endpoint in growth velocity percentile based on quartiles will be summarized by treatment group. Baseline is defined as the baseline study period (see Section 5.2: Baseline Definitions); endpoint is defined as the last 12 weeks of the double-blind treatment period. Participants with a decrease in growth velocity quartile from baseline to endpoint will be listed. Details of the calculation of these quartiles can be found in Section 11.6.3. This characterization of growth velocity will be based on all available on- and off-treatment height data.

No formal statistical analysis is planned.

7.2.3. Analysis of Growth Velocity Over the First 12 Weeks of the Double-Blind Treatment Period

Growth velocity during the first 12 weeks (~10 to 13 weeks given visit windows, [Appendix 2: Schedule of Activities](#)) of the double-blind treatment period will be analysed (Supportive Estimand XI). Regarding the intercurrent event of “*Discontinuation of Randomised Treatment*”, all available height data collected during the double-blind treatment period up to Visit 8 while the participant is on randomised double-blind

treatment will be considered. In order to be included in this analysis, a participant must have data from a Visit 8 (Week 12) stadiometric height assessment.

An analysis of covariance (ANCOVA) model, similar to the one defined for the primary analysis, will be used to estimate the mean treatment difference in growth velocities over the first 12 weeks of the double-blind treatment period. The summary measure, statistical analyses/methods (i.e., model specification, model checking and diagnostics, and model results presentation), and strategies for handling all other intercurrent events/events leading to missing data will be as described in Section 7.1: Primary Growth Analyses. By-treatment summaries of growth velocity during the baseline period and the first 12 weeks of the double-blind treatment period will also be provided. The change from baseline in growth velocity will also be summarised.

7.2.4. Growth Velocity by Gender and Ethnicity

Growth velocity during each study period will be summarized by gender (male/female), and ethnicity (Hispanic or Latino/not Hispanic or Latino). All available on- and off-treatment height data will be used regardless of the occurrence of the intercurrent events defined in Section 7.1.4.

No formal statistical analysis is planned.

7.2.5. Growth Velocity by Region (US and non-US sites)

Analyses of growth velocity by region (i.e., US vs non-US sites) will be provided (Supportive Estimand XII).

The summary measure, statistical analyses/methods (i.e., model specification, model checking and diagnostics, and model results presentation), and strategies for handling the intercurrent events/events leading to missing data will be as described in Section 7.1: Primary Growth Analyses. Separate analysis of covariance (ANCOVA) models, similar to the one defined for the primary analysis (excluding country from list of covariates), will be used to estimate the mean treatment difference in growth velocities for all participants enrolled in US sites and non-US sites, respectively. By-treatment summaries of growth velocity for all study periods (baseline, treatment, and follow-up) will be provided. The change from baseline in growth velocity will also be summarised.

7.2.6. Height Standard Deviation Scores

Height standard deviation scores will be summarized by treatment at each study visit. A box-plot illustrating the height standard deviation scores at each visit for the two treatment groups will also be provided. Details of the calculation of the height standard deviation scores can be found in Section 11.6.3. All available on- and off-treatment height data will be used.

The change from baseline (Visit 5) to endpoint (Visit 18, Week 52) in height standard deviation scores will also be summarized by treatment group. The endpoint value will be selected from available on- and off-treatment height data at Visit 18. Change from baseline will be defined as the difference between the value of the measure at the

timepoint of interest and the baseline. If either baseline or endpoint values are missing, then the change from baseline in height SDS will not be calculated.

No formal statistical analysis is planned.

7.2.7. Random Effects Model Assessing Height

A sensitivity analysis (Supportive Estimand XIII) will be provided to support the primary analysis using height (cm, via stadiometry) as the dependent variable (endpoint).

Intercurrent events will be handled as described in Section 7.1.4 for the primary analysis i.e., all available on- and off- treatment height data collected during the double-blind treatment period will be considered regardless of the occurrence of an intercurrent event.

A mixed effects ANCOVA model with baseline height (i.e., Visit 1, continuous), age at Visit 1 (continuous), gender (categorical), double-blind treatment (categorical), time (days since treatment start, continuous), and the treatment-by-time interaction as explanatory variables will be used. The intercept and the slope for the regression of height over time are assumed to be random effects (i.e., each participant has their own linear growth over time). A 95% confidence interval will be constructed for the treatment difference in mean growth velocity over the double-blind treatment period, using the estimate for the treatment-by-time interaction in the mixed effects model. The model checking and diagnostics, and strategies for handling the intercurrent events/events leading to missing data will be as described in Section 7.1: Primary Growth Analyses.

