5.4. Examination of Covariates, Other Strata and Subgroups

5.4.1. Covariates and Other Strata

The list of covariates and other strata to be used in all statistical analyses of growth velocity is as described in table below, unless otherwise specified in Section 7.

Category	Details
Strata	Study randomisation will be stratified by country. Unless otherwise specified, country will be used as a covariate in statistical models and not the randomisation stratum.
Covariates	
 • Baseline Growth Velocity • Randomised Treatment • Age at Visit 1 • Gender • Country (or group of countries, if pooling defined before unblinding)

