7.1.5.1. Statistical Methodology Specification

Endpoint / Variables

 Growth velocity (cm/yr) over the double-blind treatment period as determined by stadiometry. For details of growth velocity calculation see Section 11.6.3.
Model Specification

 The primary endpoint will be analysed using an analysis of covariance (ANCOVA) model adjusting for baseline growth velocity (continuous, see Section 5.2: Baseline Definitions), age at Visit 1 (continuous), gender (categorical), and country (categorical).

 • The primary analysis will include all available height data, regardless of any intercurrent events (defined in Section 7.1.4) that occur during the study. • Missing data will be assumed to be missing at random (MAR) and will not be imputed. The mean difference in growth velocity over the treatment period between treatments and a 95% confidence interval will also be provided.

Model Checking & Diagnostics

 • The Kenward and Roger method [Kenward, 1997] of approximating the denominator degrees of freedom and correcting for bias in the estimated variance-covariance matrix of the fixed effects will be used in the diagnostic analyses of ANCOVA models. The Kenward-Roger method will be invoked by specifying the DDFM=KR option in the PROC MIXED model statement. • Appropriate graphs will be reviewed as part of the model-checking process in order to ensure that distributional assumptions hold. Additional analyses may be considered if these assumptions are not met. These graphs will include a normal probability plot of the residuals and a plot of the residuals versus the fitted values. If there are any departures from the distributional assumptions, alternative models will be explored using appropriate transformed data.

Model Results Presentation

 • The point estimate of the mean treatment difference in growth velocity and corresponding 95% confidence interval will be presented for the comparison between treatment arms.

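### In the SAP 7.2.7 random-coefficients model only treatment interacts with time, so its treatment difference in growth velocity is effectively unadjusted, unlike the primary ANCOVA it is meant to support

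*SAP*

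**What the plan says.** SAP 7.2.7 describes the role of the model: "A sensitivity analysis (Supportive Estimand XIII) will be provided to support the primary analysis using height" as the dependent variable. The description of the fixed effects opens "A mixed effects ANCOVA model with baseline height (i.e., Visit 1, continuous), age at Visit 1 (continuous), gender (categorical), double-blind treatment (categorical), time". Time is counted in days from the start of treatment. The list then ends with its one product term, "and the treatment-by-time interaction as explanatory variables will be used". The random part is a participant-level line: "The intercept and the slope for the regression of height over time are assumed to be random effects". The 95% interval for the difference in mean growth velocity is built "using the estimate for the treatment-by-time interaction in the mixed effects model". Country and baseline growth velocity do not appear, and treatment is the only variable crossed with time.

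The primary model in SAP 7.1.5.1 (and Protocol 9.4.1.1) takes each child's fitted slope as the outcome, "adjusting for baseline growth velocity (continuous, see Section 5.2: Baseline Definitions), age at Visit 1 (continuous), gender (categorical), and country (categorical").

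SAP 5.4.1 sets a general rule: "The list of covariates and other strata to be used in all statistical analyses of growth velocity is as described in table below". The table lists baseline growth velocity, treatment, age, gender and country. The same sentence goes on to allow Section 7 to specify otherwise.

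The protocol (9.4.2.1, item 8) only names a random-coefficients analysis and gives no covariates. Protocol 4.4 gives possible differences in growth velocity between countries as one reason for stratifying randomisation by country.

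**The concern.** The quantity of interest is a difference in slopes. A covariate entered as a main effect in a model for height explains why some children are taller than others. It says nothing about why some grow faster. The model lists age and gender as adjusters, but they do not adjust the number that is reported, and country and baseline growth velocity are not in the model at all.

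Three things follow for an analysis whose job is to support the primary result:

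- It changes two things at once: the modelling approach (a joint mixed model for height in place of per-child slopes) and the covariate adjustment of the slope. A discrepancy cannot be attributed to one or the other.
- The randomisation stratum, chosen partly because growth velocity may differ by country, is left out of the slope comparison.
- Precision that the collected data could provide is given up, and the missing-at-random assumption for heights conditions on fewer variables than it could.

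**Working it through.** **The plan's own precision figure.** Protocol 9.2.1 gives SD 1.2 cm/yr, 203 per arm, 1:1 allocation and a 95% interval no wider than 0.5 cm/yr. Half-width = 1.96 × SD × √(2/n).

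- n = 200: 1.96 × 1.2 × √(2/200) = 0.235, matching the table in Protocol 9.2.2.
- n = 203: 1.96 × 1.2 × √(2/203) = 0.233, so width 0.467 cm/yr.

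The target is met without any covariate adjustment.

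**What the 7.2.7 model implies.** Written out, expected height at time t is

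(a0 + a1·Visit 1 height + a2·age + a3·gender + a4·treatment) + (b0 + b1·treatment)·t.

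The reported estimate is b1. The slope part contains treatment only, and its regressors are a subset of those in the intercept part. With complete data on a common schedule, covariates acting only on the intercept then cannot move b1: it equals the plain difference in mean per-child slopes.

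**Numerical check.** Twelve trials of 203 per arm were simulated at the SAP's scheduled height visits (Visits 5 to 9, 12, 15 and 18) and fitted by REML with random intercept and slope. Covariate effects were assumed, because the documents give none; they explain about 29% of the variance of the slope endpoint. Means over the 12 trials (cm/yr):

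| Analysis | Complete data: estimate (SE) | About 12% dropout: estimate (SE) |
|---|---|---|
| Per-child slopes, unadjusted | -0.279 (0.107) | -0.297 (0.125) |
| Mixed model, no covariates | -0.279 (0.107) | -0.282 (0.111) |
| Mixed model as in SAP 7.2.7 | -0.279 (0.107) | -0.287 (0.111) |
| 7.2.7 plus country and baseline velocity as main effects | -0.279 (0.107) | -0.286 (0.111) |
| 7.2.7 plus all four covariates by time | -0.295 (0.093) | -0.294 (0.097) |
| Primary ANCOVA | -0.295 (0.093) | -0.317 (0.113) |

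- Complete data: the 7.2.7 estimate equals the covariate-free one in every trial (largest difference about 1e-13). With dropout the two differ by at most 0.016.
- Complete data: with covariate-by-time terms, the mixed model reproduces the primary ANCOVA estimate (largest difference about 1e-13).
- Gap between 7.2.7 and the primary ANCOVA, complete data: at most 0.125, and at most 0.045 in the other eleven trials. This is chance covariate imbalance only.
- With dropout, that gap is at most 0.132 as written and at most 0.081 with the by-time terms. The remainder then reflects how incomplete slopes are weighted, which is the difference in approach that a reader would want to see.

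**Precision.** If the covariates explain a share R² of slope variance (assumed), adjustment multiplies the SE by √(1 − R²).

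- R² = 0.10: √0.90 = 0.949; the unadjusted interval is 1/0.949 = 1.05 times as wide (0.467 against 0.443 cm/yr).
- R² = 0.20: √0.80 = 0.894; the ratio is 1/0.894 = 1.12 (0.467 against 0.418 cm/yr).

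**The case against.** Much of the case for leaving the model alone is sound.

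- **No rule is broken.** A reader might infer a conflict with SAP 5.4.1, but that section defers to Section 7, and 7.2.7 lists its own covariates. The protocol is not contradicted either. What is missing is a reason. By contrast, the regional analysis in SAP 7.2.5 states openly that it drops country.
- **No bias.** A reader might infer that the slope difference is distorted. Randomisation keeps the unadjusted contrast unbiased, and since no hypothesis is tested there is no error rate to inflate.
- **The two absent covariates are not the fault in themselves.** As main effects they change nothing with complete data. Only by-time terms matter.
- **The purpose should not be over-read.** A reader might infer that the model exists to handle unequal follow-up. Section 7.2.7 says only that it supports the primary analysis.
- **The gain may be small.** Baseline velocity is a slope through two or three heights over 16 weeks. If a visit height carries an error of 0.1 to 0.3 cm (assumed), that slope has an SE of about 0.5 to 1.4 cm/yr, so it may predict later velocity weakly. The 29% in the simulation is above the 10% to 20% range used for sizing.
- **Some attribution is possible anyway.** Baseline growth velocity is to be summarised by treatment, so an imbalance would be visible. A less adjusted companion analysis can also be a legitimate choice.

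All of this limits the size of the point. It does not remove it: seeing an imbalance is not the same as adjusting for it, and nothing in 7.2.7 says that an unadjusted slope was intended.

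**Conclusion.** The point holds as an avoidable weakness in one supportive analysis. The treatment-by-time estimate in SAP 7.2.7 is effectively unadjusted, exactly so with complete data, while the primary ANCOVA adjusts for baseline growth velocity, age, gender and country. A gap between the two cannot be separated from loss of covariate adjustment, and the stratification factor plays no part in the slope comparison.

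The cost in precision is an interval about 5% or 12% wider than an adjusted version would give, if the covariates explain 10% or 20% of slope variance. Those shares are assumptions. The loss is relative to the same model with by-time terms: in the simulation with dropout, the 7.2.7 SE (0.111) was close to that of the primary ANCOVA (0.113). Even unadjusted, the planned width of 0.467 cm/yr at SD 1.2 and 203 per arm is inside the 0.5 cm/yr target.

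A reader might take this as casting doubt on the primary result. The documents do not support that: the primary estimate, its interval and the sample size do not depend on 7.2.7.

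**What to change.** In SAP 7.2.7, add baseline growth velocity and country (with the pooling already defined in SAP 5.3) to the model, and add four interactions with time: baseline growth velocity, age at Visit 1, gender and country. Keep treatment-by-time as the reported term. The slope comparison is then adjusted for the same covariates as the primary ANCOVA, and with complete data the two estimates coincide, so any remaining difference reflects the treatment of incomplete height series.

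If an unadjusted slope is intended, the SAP should say so and why, and report a matching unadjusted analysis of the per-child slopes beside it.

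The cost is a few model terms in the SAP and the program, settled before unblinding. No new data are needed.
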